5.3. Screen Failures

Subjects who fail to meet the entrance criteria at any time during the screening period are defined as screen failures. All screen failures will be recorded on the screening failure log, which documents the site number and screening number and reason(s) for screen failure. The screening failure log will be kept in the Investigator's Site File.

Re-screening/re-assessment outside the Screening period will be possible on a case-by-case basis following approval by the principal investigator. Subjects allowed to be re-screened, will be determined a screen failure after the second screening confirmed the subject is ineligible.

5.4 Registration Procedures

Patients will be registered after meeting all entry requirements and providing a signed informed consent document. The date of the PI/treating physician signature on the eligibility checklist confirming that the patient meets the eligibility criteria is the registration date.

5.4.1 Enrollment

Eligible patients will be enrolled on study centrally at Moffitt Cancer Center by the Study Coordinator.

When all required test results are available, complete the eligibility checklist and provide the checklist and the supporting documentation to the IRB approved investigator for review and sign-off. Once the investigator (or Sub-Investigator) has signed the eligibility checklist, enrollment may proceed.

Following enrollment, patients should begin protocol treatment within 7 business days. Issues that would cause treatment delays should be discussed with the Principal Investigator.

6. STUDY INTERVENTION

Study intervention is defined as any investigational intervention(s), marketed product(s), placebo, or medical device(s) intended to be administered to a study subject according to the study protocol.

6.1. Study Intervention(s) Administered

On days when both intratumoral tavo and IV nivolumab are administered, every effort will be made not to administer the treatments to the same arm or location. It is recommended that tavo will be administered first.

	tavo-EP		Nivolumab
Intervention Name	Tavokinogene telseplasmid	Electroporation	Nivolumab
Type	Biologic	Device	Biologic
Dose Formulation	1.5 mL vials at a concentration of 0.5 mg/mL		4 mL and 10 ml vials at a concentration of 10 mg/mL solution for IV infusion
Unit Dose Strength(s)	mg		mg
Dosage Level(s)	Tavo will be injected on Days 1 and 8 every 4 weeks at a dose volume of $\frac{1}{4}$ of the calculated lesion volume with a minimum dose volume per lesion of 0.1 mL for lesions of volume $<0.4 \text{ cm}^3$ NOTE: At the discretion of the treating physician investigator and as discussed with the patient as a means of maximizing local effects of Tavo, an optional additional cycle of Tavo can be administered during the 3rd week (Day 15) of each of the 3 neoadjuvant cycles in the absence of limiting toxicities.	See Section 6.1.1.	480 mg Q4W over 30 minutes NOTE: Every effort will be taken to ensure that the infusion duration be as close to 30 minutes as possible. However, given the variability of infusion pumps from site to site, a window between -5 minutes and +10 minutes is permitted (i.e., infusion time of 25 to 40 minutes). In patients who poorly tolerate the planned infusion time, the infusion time may be extended as clinically indicated by the treating team. Future infusion times may also be extended as determined to be clinically indicated by the treating physician.
Route of Administration	Intratumoral injection	Electroporation	IV infusion

	tavo-EP		Nivolumab
IMP and NIMP			Approved
Sourcing	GMP-grade tavo is manufactured, packaged and provided centrally on behalf of the study supporter.	Provided centrally by the study supporter.	Provided locally by the study site.
Packaging and Labeling	Study Intervention will be provided in vials. Each vial will be labeled as required per country requirement.	See Section 6.1.1.	Study Intervention will be provided in vials. Each vial will be labeled as required per country requirement.
Current/Former Name(s) or Alias(es)	ImmunoPulse tavo Tavokinogene telseplasmid		OPDIVO

6.1.1. Medical Devices

The OMS, a medical EP device system, consists of 3 main components: (1) an Electroporation Generator that generates electric pulses, (2) a sterile Applicator Tip containing needle array, and (3) an Applicator Handle that connects to the Electroporation Generator at the proximal end and connects to the Applicator Tip at the distal end. The Applicator Tip contains a circular 6 needle array and comes in two models characterized by the needle array diameter: 0.5 cm and 1.0 cm. The needle length is 1.5 cm for both models and the needle insertion depth is adjustable by the user between 0 and 1.5 cm. An OncoSec Printer may be optionally used to generate a real-time event log of the electroporation treatment information used during the treatment.

Upon user activation of the attached Foot Switch, the OMS Electroporation Generator delivers controlled electrical pulses in a square wave pulse pattern yielding optimal transmembrane potential for electroporation to occur. EP pulses occur between 6 hexagonal opposing needle electrodes. After the first pulse, the polarity between the opposing needle electrode pairs is reversed and the needle pair is pulsed again. After the initial paired pulse, the pulse delivery is rotated clockwise to the next opposing needle pairs until a total of 6 pulses are delivered to complete the EP sequence.

OncoSec filed a Device Master File (MAF) with the Food and Drug Administration (FDA) with information on the electrical safety and electromagnetic compatibility, biocompatibility, sterility, software, packaging, etc.

Additional details regarding handling of the device are provided in the OncoSec Medical System Operator's Manual.

6.2. Preparation/Handling/Storage/Accountability

1. The investigator or designee must confirm appropriate temperature conditions have been maintained during transit for all study intervention received and any discrepancies are reported and resolved before use of the study intervention.
2. Unopened drug product (tavo) sterile vials should be stored in the packaging received from OncoSec in a secure, continuously temperature monitored and alarmed freezer in

the pharmacy or other appropriate secure location at a nominal temperature of -20°C. Temperature variation is allowed to a maximum temperature of -10°C. Any temperature excursions greater (warmer) than -10°C must be reported to the principal investigator and later to OncoSec. Refer to the Pharmacy Manual.

3. The OMS Applicator and Tips will be supplied by OncoSec and should be stored in ambient conditions in a restricted area with limited access and may only be used on subjects who have been properly consented and enrolled into the investigational studies. Refer to the Operators Manual.
4. Only subjects enrolled in the study may receive study intervention and only authorized site staff may supply or administer study intervention. All study intervention must be stored in a secure, environmentally controlled, and monitored (manual or automated) area in accordance with the labeled storage conditions with access limited to the investigator and authorized site staff.
5. Please refer to the Study Pharmacy Manual for tavo plasmid preparation and storage instructions. Briefly, Tumor size will be used to calculate the total dose per lesion and per subject. The number of vials needed for each intratumoral injection must be thawed at room temperature for approximately 5-10 minutes and mixed vigorously prior to drawing the solution using a sterile tuberculin syringe of appropriate size (0.3 mL to 10 mL), with a 25-gauge to 30-gauge 5/8-inch needle and needle cap. Additional plasmid solution can be withdrawn as needed to prime the syringe and deliver accurate dose(s) to the subject. Each treatment syringe should be visually inspected prior to injection, checking that the suspension is homogeneous. If the suspension does not appear homogeneous, the syringe should be discarded and new plasmid for treatment prepared. Unused portions of each vial will be discarded into approved biohazard containers and disposed of as per institutional requirements. The prepared formulation must be administered within 8 hours after thawing at room temperature.
6. Nivolumab will be prepared per manufacturer's instructions and should be stored as per the product's package insert.
7. The investigator is responsible for study intervention accountability, reconciliation, and record maintenance (i.e., receipt, reconciliation, and final disposition records).

6.3. Study Intervention Compliance

Subject compliance with study intervention will be assessed at each visit. Compliance will be based on accountability records and an inventory of used/unused supplies. Deviation(s) from the prescribed dosage regimen should be recorded in the eCRF.

6.4. Concomitant Therapy

All treatments that the Investigator considers necessary for a subject's welfare may be administered at the discretion of the Investigator in keeping with the community standards of medical care.

Any medications that belong to corticosteroids, immunosuppressant and/or hormonal replacement therapies that the subject is receiving at the time of enrollment or receives during the study must be recorded along with:

- Reason for use
- Dates of administration including start and end dates
-

Both local and systemic analgesics and anxiolytics, as well as topical and/or injected anesthetics are recommended prior to the intratumoral tavo-EP procedure. Other methods, including conscious sedation, are also permitted and will be employed per Investigator discretion and standard institutional practices. Other concomitant medication may be considered on a case-by-case basis by the Investigator in consultation with the Principal Investigator.

The Principal Investigator should be contacted if there are any questions regarding concomitant or prior therapy.

6.4.1. Prohibited Concomitant Medications

Medications or vaccinations specifically prohibited in the exclusion criteria are not allowed during the ongoing study. If there is a clinical indication for any medication or vaccination specifically prohibited during the study, discontinuation from study therapy or vaccination may be required. The Investigator should discuss any questions regarding this with the Principal Investigator. The final decision on any supportive therapy or vaccination rests with the Investigator and/or the subject's primary physician. However, the decision to continue the subject on study therapy or vaccination schedule requires the mutual agreement of the Investigator, the Principal Investigator and the subject.

Listed below are specific restrictions for concomitant therapy or vaccination during the course of the study:

- Antineoplastic -systemic chemotherapy or biological therapy
- Immunotherapy not specified in this protocol
- Investigational agents other than nivolumab and tavo-EP
- Radiation therapy (Note: Radiation therapy to a symptomatic solitary lesion or to the brain may be allowed at the Investigator's discretion)
- Live vaccines within 30 days prior to the first dose of study treatment and while participating in the study. Examples of live vaccines include, but are not limited to, the following: measles, mumps, rubella, chicken pox, yellow fever, rabies, BCG, and typhoid (oral) vaccine. Seasonal influenza vaccines for injection are generally killed virus vaccines and are allowed; however intranasal influenza vaccines (e.g., Flu-Mist®) are live attenuated vaccines, and are not allowed.

- Systemic glucocorticoids (in dosing exceeding 10 mg daily of prednisone equivalent) for any purpose other than to modulate symptoms from an AE that is suspected to have an immunologic etiology. The use of physiologic doses of corticosteroids may be approved after consultation with the principal investigator. *Note: Topical steroids are permitted. Inhaled steroids are allowed for management of asthma.*

Subjects who, in the assessment by the Investigator, require the use of any of the aforementioned treatments for clinical management should be removed from the study.

All treatments that the Investigator considers necessary for a subject's welfare may be administered at the discretion of the Investigator in keeping with the community standards of medical care.

The Exclusion Criteria describes other medications that are prohibited in this study.

There are no prohibited therapies during the post-treatment follow-up period.

6.5. Intervention after the End of the Study

No study extension is planned.

6.6. Stopping Rules and Toxicity Management Guidelines

6.6.1. Tavo

The concentration of tavo is 0.5 mg/mL. Decision in the total number of injected lesions will be made at the discretion of the Principal Investigator and/or treating physician. Considerations will include the number of tumor lesions accessible for injection and electroporation and each subject's ability to tolerate the procedure.

Death(s) within 30 days of last dose of combination treatment on study, that are considered at least possibly related to study treatment, will result in temporary suspension of enrollment and dosing until assessed by **PMC**.

If a subject experiences a Grade 4 hematological or non-hematological AE, combination treatment of tavo-EP and nivolumab will be discontinued until toxicity resolves to Grade ≤ 1 or baseline levels. Consult the principal investigator if a subject experiences a Grade 3 hematological or non-hematological AE that is not resolved within 1 treatment cycle. If the AE resolves during the cycle such that Days 1 and 8 may take place within the allowed ± 2 -day window, then continuation of treatment may take place. Alternatively, combined treatment will be restarted on Day 1 of the next scheduled treatment cycle. The next treatment cycle may begin sooner than scheduled per Investigator's discretion following discussion with the principal investigator. If the hematological toxicity does not resolve within 12 weeks of last treatment, permanent discontinuation should be considered for any severe or life-threatening event. Subject missing 2 intratumoral tavo-EP treatments in the neoadjuvant phase will be allowed to continue nivolumab (as monotherapy) treatment up to a total of 12 cycles (3 combination cycles and 9 monotherapy cycles). Missed doses are permitted for inclement weather/acts of nature.

Please notice that tissue ulceration or cellulitis infections related to Tavo injection and/or EP are included under Events of Clinical Interest. Further, the occurrence of any > grade 2 skin ulcerations must lead to the discontinuation of injection and EP at that site.

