6.6.2. Nivolumab

It is recommended to continue treatment with nivolumab for clinically stable subjects with initial evidence of disease progression until disease progression is confirmed.

Dose escalation or reduction is not recommended. Dosing delay or discontinuation may be required based on individual safety and tolerability. Guidelines for permanent discontinuation or withholding of doses are described in [Table 1](#). Detailed guidelines for the management of immune-related adverse reactions are described in Nivolumab package insert.

If during the neoadjuvant phase, nivolumab is withheld or discontinued, tavo-EP can be administered as monotherapy (up to 3 4-week cycles) after discussion with principal investigator.

Table 1 Recommended treatment modifications for nivolumab

Immune-related adverse reaction	Severity	Treatment modification
Immune-related pneumonitis	Grade 2 pneumonitis	Withhold dose(s) until symptoms resolve, radiographic abnormalities improve, and management with corticosteroids is complete
	Grade 3 or 4 pneumonitis	Permanently discontinue treatment
Immune-related colitis	Grade 2 diarrhea or colitis	Withhold dose(s) until symptoms resolve and management with corticosteroids, if needed, is complete
	Grade 3 diarrhea or colitis	Withhold dose(s) until symptoms resolve and management with corticosteroids is complete
	Grade 4 diarrhea or colitis	Permanently discontinue treatment
Immune-related hepatitis	Grade 2 elevation in aspartate aminotransferase (AST), alanine aminotransferase (ALT), or total bilirubin	Withhold dose(s) until laboratory values return to baseline and management with corticosteroids, if needed, is complete
	Grade 3 or 4 elevation in AST, ALT, or total bilirubin	Permanently discontinue treatment
Immune-related nephritis and renal dysfunction	Grade 2 or 3 creatinine elevation	Withhold dose(s) until creatinine returns to baseline and management with corticosteroids is complete
	Grade 4 creatinine elevation	Permanently discontinue treatment

Immune-related adverse reaction	Severity	Treatment modification
Immune-related endocrinopathies	Symptomatic Grade 2 or 3 hypothyroidism, hyperthyroidism, hypophysitis, Grade 2 adrenal insufficiency Grade 3 diabetes	Withhold dose(s) until symptoms resolve and management with corticosteroids (if needed for symptoms of acute inflammation) is complete. Treatment should be continued in the presence of hormone replacement therapy ^a as long as no symptoms are present

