	Grade 4 hypothyroidism Grade 4 hyperthyroidism Grade 4 hypophysitis Grade 3 or 4 adrenal insufficiency Grade 4 diabetes	Permanently discontinue treatment
Immune-related skin adverse reactions	Grade 3 rash	Withhold dose(s) until symptoms resolve and management with corticosteroids is complete
	Grade 4 rash	Permanently discontinue treatment
	Stevens-Johnson syndrome (SJS) or toxic epidermal necrolysis (TEN)	Permanently discontinue treatment (see section 4.4)
Other immune-related adverse reactions	Grade 3 (first occurrence)	Withhold dose(s)
	Grade 3 myocarditis	Permanently discontinue treatment
	Grade 4 or recurrent Grade 3; persistent Grade 2 or 3 despite treatment modification; inability to reduce corticosteroid dose to 10 mg prednisone or equivalent per day	Permanently discontinue treatment

Note: Toxicity grades are in accordance with National Cancer Institute Common Terminology Criteria for Adverse Events Version 5.0 (NCI-CTCAE v5.0).

Source: Nivolumab package insert 2018

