7.1.1. Temporary Discontinuation

See Section 6.6 for stopping rules and toxicity management.

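### Section 6.6.1 makes every Grade 4 stop of nivolumab temporary, with no exception for the immune-related events after which Table 1 stops it permanently

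*Combined protocol and SAP*

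**What the plan says.** Section 6.6.1 (Tavo) covers every Grade 4 event, hematological or not. In that case "combination treatment of tavo-EP and nivolumab will be discontinued until toxicity resolves to Grade" 1 or lower, or baseline. It then asks for consultation on a Grade 3 event that has not resolved within a cycle. After that it allows treatment to go on if the event resolves inside the visit window, and otherwise: "Alternatively, combined treatment will be restarted on Day 1 of the next scheduled treatment cycle".

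Section 6.6.2 (Nivolumab) has its own rules: "Guidelines for permanent discontinuation or withholding of doses are described in" Table 1. It adds that "Dosing delay or discontinuation may be required based on individual safety and tolerability", and refers to the package insert for managing immune-related reactions. If nivolumab is withheld or stopped in the neoadjuvant phase, "tavo-EP can be administered as monotherapy (up to 3 4-week cycles) after discussion with principal investigator". Table 1 lists the events that end nivolumab for good. Its row for other immune-related reactions includes "Grade 4 or recurrent Grade 3; persistent Grade 2 or 3 despite treatment modification".

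Section 7.1.1 does not choose between the two: "See Section 6.6 for stopping rules and toxicity management". Section 7.1 likewise points to Section 6.6 as a whole.

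**The concern.** A subject with Grade 4 immune-related colitis that resolves is on a temporary hold under 6.6.1 and a permanent nivolumab stop under Table 1. Both rules name nivolumab and both apply to that event. Whether an anti-PD-1 antibody may be given again after a Grade 4 immune-related reaction should be stated, not left for the treating team to infer.

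The gap also affects reporting. Section 9.4.1 promises an account of all identified protocol violations. A nivolumab dose given after a resolved Grade 4 immune-related event complies with 6.6.1 and contradicts Table 1, so it cannot be classified consistently until one rule is given precedence.

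**Working it through.** The plan states no figure on this point, so the check is a comparison of texts followed by a count of doses.

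**1. Grade 4 events in Table 1.** Action on nivolumab at Grade 4, by category:

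| Table 1 category | Table 1 | Section 6.6.1 |
|---|---|---|
| Pneumonitis | permanent stop (also Grade 3) | hold until resolved |
| Colitis | permanent stop | hold until resolved |
| Hepatitis | permanent stop (also Grade 3) | hold until resolved |
| Nephritis | permanent stop | hold until resolved |
| Endocrinopathies | permanent stop (adrenal insufficiency also Grade 3) | hold until resolved |
| Skin | permanent stop | hold until resolved |
| Other | permanent stop (myocarditis also Grade 3) | hold until resolved |

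The two differ in 7 of 7 categories.

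**2. Exceptions inside 6.6.1.** Permanent discontinuation of treatment is mentioned only for hematological toxicity unresolved at 12 weeks, and there it is something to consider. The skin-ulceration rule ends injection and electroporation at that site only. There is no immune-related exception and no reference to Table 1.

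**3. Precedence.** No sentence in Sections 4.3.3, 6.6, 7.1, 7.2 or 10.3.5 ranks 6.6.1 against Table 1. The strength of the wording does not settle it in favor of Table 1 either: the table is titled as recommendations and introduced as guidelines, while the restart in 6.6.1 is worded as something that will happen.

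**4. Scheduled doses at issue.** Inputs from Sections 1.1 and 4.1: 3 neoadjuvant cycles, one nivolumab dose per cycle on Day 8. Assume the event follows that cycle's nivolumab dose, resolves before the next cycle, and treatment restarts there. Neoadjuvant doses left after an event in Cycle k = 3 − k:

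- Cycle 1: 3 − 1 = 2
- Cycle 2: 3 − 2 = 1
- Cycle 3: 3 − 3 = 0
- Under Table 1: 0 in every case

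These are counts of what the restart wording provides for on the base schedule. They leave out the additional neoadjuvant cycles that Section 1.1 allows before a delayed surgery. The documents give no rate of Grade 4 immune-related events for this regimen, so no expected number of subjects can be given.

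**The case against.** The best defense is that Section 6.6 should be read as a whole. Section 6.6.1 is headed for tavo and sets a general hold. Section 6.6.2 is headed for nivolumab, sends permanent discontinuation to Table 1, refers immune-related management to the package insert, and already provides for a subject who stops nivolumab and goes on with tavo-EP alone. Section 4.3.3 says nivolumab follows the label, and Table 1 cites the package insert as its source. On the ordinary principle that the specific rule governs, Table 1 wins. This is good evidence of intent, and it stands. It does not remove the conflict, because 6.6.1 itself directs nivolumab dosing and nothing subordinates it.

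The restart sentences follow the Grade 3 sentence, so it is not certain that the event they refer to is Grade 4. That is a fair point. But the Grade 4 sentence alone makes the stop last only until resolution, which already contradicts Table 1.

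Investigator judgment on removal from treatment (Section 10.3.5), withdrawal for significant safety risk (7.2) and discontinuation for individual tolerability (6.6.2) all protect subjects in part. They leave the decision to judgment and do not rank the two rules.

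A reader might infer a second, larger route from the sentence that a subject missing two neoadjuvant tavo-EP treatments "will be allowed to continue nivolumab (as monotherapy) treatment up to a total of 12 cycles (3 combination cycles and 9 monotherapy cycles"). A hold over Days 1 and 8 of one cycle is two missed treatments, so a Grade 4 hold might seem to open the way to nivolumab through the adjuvant phase. The text does not support this. The sentence says that missing tavo-EP does not by itself end nivolumab. It mentions neither adverse events nor grades, is followed by a remark about weather, and does not cancel a nivolumab-specific stop. No dose count should rest on it.

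A reader might also infer that the conflict governs new events on adjuvant nivolumab. It does not. The 6.6.1 hold concerns the combination, and a new Grade 4 immune-related event on monotherapy falls under 6.6.2 and Table 1 with no competing restart rule.

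**Conclusion.** The conflict is real but limited. Followed literally, 6.6.1 permits nivolumab to resume after Grade 4 events for which Table 1 stops it permanently, in 7 of 7 categories. The difference is at most 2 scheduled neoadjuvant doses per subject on the base schedule, under the timing assumptions stated with the count. Table 1 was very probably meant to govern, but the protocol does not say so.

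The notes to Section 1.3, effective July 26, 2023, say that all patients have completed the neoadjuvant phase, so the conflict is now mainly retrospective. What could still matter is a subject who had such an event in the neoadjuvant phase and is still receiving adjuvant nivolumab; the notes do not say that the adjuvant phase is complete. No re-dosing is documented, and none should be inferred. The pathologic response endpoint, the sample size and the Simon decision rule are unaffected. The correction should be made, chiefly so that the safety rule is unambiguous and past doses can be classified.

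**What to change.** Add one sentence to Section 6.6.1: *Restart or continuation of nivolumab under this section does not apply where Table 1 specifies permanent discontinuation; in that case only tavo-EP may resume, as in 6.6.2.* Because it refers to Table 1 and not to a grade, it also covers the Grade 3 events that Table 1 treats as permanent stops.

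From existing dosing and adverse event data, list any nivolumab dose given after an event for which Table 1 specifies permanent discontinuation. Apply Table 1 to any such subject still on adjuvant nivolumab.

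The cost is a minor protocol amendment with IRB review (Section 10.1.1 covers amendments) and one listing. No new data collection is needed.
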